# Figure 6.1.1-2. ENTACT Septal Stapler (current design) Mechanism

# 6.1.2 ENTACT Septal Stapler (Previous generations)

The ENTACT stapler originally launched in 2009 by ENTrigue Surgical Inc before the acquisition by ArthroCare (now S+N). Feedback from the market was collected, and changes to the device were implemented in 2010 and 2012. The changes were implemented to streamline the manufacturing process and improve device functionality.

# 6.1.3 ENTACT Septal Stapler (Next Generation)

The Next Generation device seeking CE marking utilizes the same implant as the current version of ENTACT Septal Stapler. The implant's material composition, geometry, and processing remain unchanged. The delivery system is very similar in the new device, with a few changes to the delivery part of the device in order to enhance manufacturability and reduce the cost of goods. A comparison of the current vs. new design ENTACT Septal Stapler can be found in **Table 6.1.3-1**.

# Table 6.1.3-1 Comparable Device Table

	Current Design	New Design	Impact of
	Previous generation	Next Generation	Differences
Implant Design	The ENTACT staple is ~4.6 mm long, ~2.5 mm wide and ~0.55 mm thick in the shaft middle but ~0.7 mm thick at the top and bottom tabs.		None
Implant composition	Polymer: L-Lactide/Glycolide Conte Inherent Viscosity Water content: D&C Violet #2: Monomer Content:	L-lactide-co-glycolide 5/95 ratio 1.6 ± 0.4 dL/g ≤ 0.5% 0 – 0.10% wt% <5.0% total	None
Height of Distal head Width of Distal head	8.3mm	7.0mm	None,
Counter tension arm	6.0mm	4.9mm	justification below
material	Polycarbonate and 17-4 Stainless steel	(polyacrylamide with 50% glass fiber)	None, justification below
Implant channel material	304 Stair	lless steel	None
Holding block material	Medical grade	Polycarbonate	None
Pins in channel material	18-8 Stainless steel	300 Series Stainless steel	None, justification below
Push ribbon material	Nit	inol	None
Pull ribbon material	Nit	inol	None
Sterilization	Gamma	Irradiation	None
	Current Design Previous Generation	New Design Next Generations	Impact of Differences
Packaging configuration	Foil pouc	ch, Carton	None

#### CONFIDENTIAL AND PROPRIETARY

Study Protocol	>∕ smith&nephew
A prospective, multi-center, single arm PMCF study to evaluate the safety and performance of ENTACT™ (Next Generation) resorbable septal staple system for septoplasty	Number: ENTACT.ENT.PRO.SEP.2019.05
	Version: 2.0, 27Aug2020
	Page: Page 31 of 94

Indications	The ENTACT Septal Stapler delivers implantable septal staples which are intended to connect internal tissues to aid healing and for approximation of soft tissues during nasal septal surgery	None
Surgical Technique/ Deployment Methods	1. If there is no cartilage between the mucoperichondrial flaps, the staples can be delivered unilaterally. If cartilage is present, stapling the flaps bilaterally may be considered.	None
	2. Remove protective silicone cover from the distal end of the stapler.	
	3. Unfold and gradually remove pull tab from the distal end of the stapler.	
	4. Insert the distal tip of the ENTACT Septal Stapler in the nose, one arm in each nostril.	
	5. Plan placement of staples, so they are spaced approximately 15 mm apart or as deemed necessary from each other.	
	6. Place the stapler against the mucoperichondrial flap, keeping stapler as perpendicular to the tissue surface as possible and depress handle until an audible click is heard to deploy each staple.	
	7. Release handle until a second audible click is heard before repositioning the distal tip of the stapler.	
	8. If necessary, repeat this procedure in the opposite cavity.	
	9. Visually inspect both nasal cavities to assure adequate approximation and sufficient penetration of the staples.	
	10. The device is empty when the blue indicator within the clear implant housing is against the distal tip. Firing an empty device will cause the implant guide needle to pierce and make a hole in the septum without placement of an implant.	
	staples.	

Study Protocol	% smith&nephew
A prospective, multi-center, single arm PMCF study to evaluate the safety and performance of ENTACT ™ (Next Generation) resorbable septal staple system for septoplasty	Number: ENTACT.ENT.PRO.SEP.2019.05
	Version: 2.0, 27Aug2020
	Page: Page 32 of 94

The Next Generation Smith+Nephew ENTACT Septal Stapler described in **Table 6.1.3-1** can be considered comparable to the Previous Generation of the ENTACT Septal Stapler for the following reasons:

- Clinical
  - Both devices are indicated for connecting internal tissues to aid healing and for approximation of soft tissues during nasal septal surgery.
- Technical
  - Both devices enable septal flap closure through the delivery of resorbable implants.
  - The mechanism and kinematics used to deploy the staples are the same in both devices. The principles of operation are identical.
- Biological:
  - The materials utilized in the implant, implant channel, holding block, and the push and pull ribbon are exactly the same in both devices.

Below are the identified differences between the Next and Previous Generation ENTACT Septal Stapler with a rationale for acceptance of those differences.

- Clinical:
  - None, both devices have the same intended use.
- Technical:
  - Distal head changes - the height of the distal head was reduced from 8.3mm to 7.0mm, and the width was reduced from 6.0mm to 4.9mm. The minor design changes to improve surgical access do not affect the intended use of the device.

This document contains information that is confidential and proprietary to Smith + Nephew PLC and Smith + Nephew, Inc. and is intended for use only by Smith + Nephew and its manufacturer. It shall not be reproduced or copied in whole or in part, nor shall the contents be disclosed by any means without prior written permission from Smith + Nephew, nor shall anyone make any use of it that is contrary to the expressed or implied wishes of Smith + Nephew.

Study Protocol	>∕smith&nephew
A prospective, multi-center, single arm PMCF study to evaluate the safety and performance of ENTACT ™ (Next Generation) resorbable septal staple system for septoplasty	Number: ENTACT.ENT.PRO.SEP.2019.05
	Version: 2.0, 27Aug2020
	Page: Page 33 of 94

# Figure 6.1.3-1 Distal head changes from current device (top) to new device (bottom)

- Biological
  - Counter tension arm - There are no impact of differences in material for the counter tension arm as PARA has mechanical properties close to stainless steel, and is commonly used in medical devices. Smith+Nephew has conducted both biological and mechanical testing, and has objective evidence that the new device meets all the same requirements as the current device.
  - Pins in Channel - There are no impact of differences in material for the pins in channel as 18-8 stainless steel are in the 300 series stainless steel family, with different naming conventions. These designations are considered interchangeable as 300 Series stainless steels are required to contain 18% chromium and 8% nickel and 18-8 means the steel is 18% chromium and 8% nickel. Smith+Nephew has conducted both biological and mechanical testing, and has objective evidence that the new device meets all the same requirements as the current device.

This document contains information that is confidential and proprietary to Smith + Nephew PLC and Smith + Nephew, Inc. and is intended for use only by Smith + Nephew and its manufacturer. It shall not be reproduced or copied in whole or in part, nor shall the contents be disclosed by any means without prior written permission from Smith + Nephew, nor shall anyone make any use of it that is contrary to the expressed or implied wishes of Smith + Nephew.

Study Protocol	>∕; smith&nephew
A prospective, multi-center, single arm PMCF study to evaluate the safety and performance of ENTACT™ (Next Generation) resorbable septal staple system for septoplasty	Number: ENTACT.ENT.PRO.SEP.2019.05 Version: 2.0, 27Aug2020
	Page: Page 34 of 94

The minor differences between the comparable device previous generation ENTACT Septal Stapler and Next Generation ENTACT Septal Stapler, are expected to have no impact to the safety of the devices. As these devices as considered comparable, we expect similar clinical safety and performance outcomes.

Refer to the ENTACT Septal Stapler Instructions for Use for more information.

- Do NOT place a staple where the needle path is obstructed or a collision with any object may occur.
- Do NOT use the staple on tissue which is too thick or hard (such as bone) to permit an effective tissue capture.
- Do NOT use with patients in whom radiopacity is necessary or desired since ENTACT staples are radiotransparent.
- Do NOT use in patients in whom prolonged tissue approximation beyond that needed for normal tissue closure is necessary or desired.

# 6.1.4 Material Specification Staple Implant

Desc

Counter tension arm

The staple implant configuration is composed of the absorbable copolymer 5% Poly-L-lactide / 95% Polyglycolide. During the molding process, a violet colorant is introduced. The D&C Violet #2 is a colorant additive (~ 0.05 wt%) to make the implants easier for the doctor to visualize upon placement in the tissue. As previously stated, the ENTACT staple used in both the current and subject devices are identical.

	Existing Device	New Device Meterial	Categorization	
ription	Material	New Device Material	Nature of Body	Contact
(Previe	(Previous Generation)	(Next Generation)	Contact	Duration

Ixef 1022 PARA

50% glass fiber)

|--|

CONFIDENTIAL AND PROPRIETARY
This document contains information that is confidential and proprietary to Smith + Nephew PLC and Smith + Nephew, Inc. and is
intended for use only by Smith + Nephew and its manufacturer. It shall not be reproduced or copied in whole or in part, nor shall the
contents be disclosed by any means without prior written permission from Smith + Nephew, nor shall anyone make any use of it that
is contrary to the expressed or implied wishes of Smith + Nephew.

Polycarbonate and 17-4 (polyacrylamide with

Medical grade

Stainless steel

Study Protocol	% smith&nephew
A prospective, multi-center, single arm PMCF study to evaluate the safety and performance of ENTACT™ (Next Generation) resorbable septal staple system for septoplasty	Number: ENTACT.ENT.PRO.SEP.2019.05
	Version: 2.0, 27Aug2020 Page: Page 35 of 94

Implant channel	304 Stainless steel		Surface contact – skin	Transient
Holding block	Medical grade Polycarbonate		and mucosal	
Pins in channel	18-8 Stainless steel	300 Series Stainless steel	membranes	
Push ribbon Pilot Hole ribbon		Nitinol		

# 6.1.5 Ancillary Product

Not applicable (NA)

# 6.2 **PRODUCT USE**

Refer to IFU for detailed information on contraindications, warnings, precautions, intended users, physician training requirements, instructions for use, and device disposal.

Sites that are familiar with the use of ENTACT Septal Stapler will be selected; no additional training is required.

# 6.3 PACKAGING AND LABELING

Packaging and labeling will be prepared to meet regulatory requirements.

# 6.3.1 Labeling of Investigational Product

All devices used in this study will be procured in standard commercial packaging, ordered via normal and customary Smith + Nephew procedures, and managed per study site processes.

# 6.4 **PRODUCT ACCOUNTABILITY PROCEDURES**

The investigational product (IP) is not provided by S+N for this post-market study, and no product accountability procedures will be applied.

This document contains information that is confidential and proprietary to Smith + Nephew PLC and Smith + Nephew, Inc. and is intended for use only by Smith + Nephew and its manufacturer. It shall not be reproduced or copied in whole or in part, nor shall the contents be disclosed by any means without prior written permission from Smith + Nephew, nor shall anyone make any use of it that is contrary to the expressed or implied wishes of Smith + Nephew.

Study Protocol	Smith&nephew
A prospective, multi-center, single arm PMCF study to evaluate the safety and performance of ENTACT™ (Next Generation) resorbable septal staple system for septoplasty	Number: ENTACT.ENT.PRO.SEP.2019.05
	Version: 2.0, 27Aug2020
	Page: Page 36 of 94

# 6.5 **SURGICAL TECHNIQUE**

All study-related procedures with the ENTACT Septal Stapler must be performed according to the recommended surgical technique described in the protocol or in a separate instructional document and product labeling (e.g., IFU) as applicable.

Surgeons selected to participate in this study will be familiar with using the ENTACT Septal Staples system.

# 7. SUBJECT ENROLLMENT AND WITHDRAWAL

# 7.1 **SUBJECT POPULATION**

The study will consist of five visits, including screening/pre-operative, operative, and follow up visits at 5, 21, and 42 days post-surgery. The need for these visits as part of the study will be made clear in the consent form and will be fully explained at the time of recruitment.

Forty (40) individuals to be approached for participation in this study awho are receiving or seeking care for nasal septal obstructions. Subjects will be enrolled up to 3 sites across the United States.

Ethnic minorities are classed as vulnerable subjects according to International Organization for Standardization (ISO) 14155:2011; however, they will be included providing they meet other inclusion criteria, and there are informed consent documents and personnel to lead the consent process in a language that is fully understood by the potential subject.

# 7.2 INCLUSION CRITERIA

The patient will be eligible for the study if he or she meets all of the following inclusion criteria at the baseline screening:

This document contains information that is confidential and proprietary to Smith + Nephew PLC and Smith + Nephew, Inc. and is intended for use only by Smith + Nephew and its manufacturer. It shall not be reproduced or copied in whole or in part, nor shall the contents be disclosed by any means without prior written permission from Smith + Nephew, nor shall anyone make any use of it that is contrary to the expressed or implied wishes of Smith + Nephew.
Study Protocol	% smith&nephew	
A prospective, multi-center, single arm PMCF study to evaluate the safety and performance of ENTACT™ (Next Generation) resorbable septal staple system for septoplasty	Number: ENTACT.ENT.PRO.SEP.2019.05	
	Version: 2.0, 27Aug2020	
	Page: Page 37 of 94	

- 1. Able and willing to give informed consent by voluntarily providing written informed consent in accordance with governing Institutional Review Board (IRB);
- 2. Clinically significant deviation of the nasal septum;
- 3. Willing and able to make all required study visits;
- 4. Able to read and understand the approved informed consent form and patient reported outcome assessments (written and oral).

## 7.3 Exclusion Criteria

The patient will be ineligible for the study if he or she meets any of the following exclusion criteria at the baseline screening or during surgery:

- 1. Prolonged tissue approximation beyond that needed for normal tissue closure is necessary or desired;
- 2. Traditional suturing techniques is necessary;
- 3. Radiopacity is necessary or desired since ENTACT septal staples are radiotransparent;
- 4. Known to be allergic to foreign body of materials of investigational product;
- 5. Concomitant procedures other than turbinectomy, turbinate reduction and/or sinus surgery;
- 6. Pregnancy at time of procedure;
- 7. Presence of infection at the site;
- 8. Severe drug and alcohol abusers;
- 9. Autoimmune disease deemed clinically significant by Principal Investigator.

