### 7.6 ENROLLMENT

Subjects for whom the consent process has been completed and have been treated with the study product are considered enrolled.

Subjects will be assigned a Subject ID at the time of consent.

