### 7.7 SCREEN FAILURES

Subjects who have provided consent, completed screening, and for any reason do not meet the eligibility criteria, were not enrolled by the Investigator for any reason, or withdraw consent for any reason prior to enrollment, will be considered a consented screen failure. For these subjects, record the reason for screen failure on the Screening and Enrollment Log and complete the End of Study Case Report Form (CRF) documenting the primary reason for discontinuation. Consented screen failures will be replaced without limit by newly enrolled subjects.

This document contains information that is confidential and proprietary to Smith + Nephew PLC and Smith + Nephew, Inc. and is intended for use only by Smith + Nephew and its manufacturer. It shall not be reproduced or copied in whole or in part, nor shall the contents be disclosed by any means without prior written permission from Smith + Nephew, nor shall anyone make any use of it that is contrary to the expressed or implied wishes of Smith + Nephew.

Study Protocol	Smith&nephew
A prospective, multi-center, single arm PMCF study to evaluate	Number:
the safety and performance of ENTACT™ (Next Generation) resorbable septal staple system for septoplasty	ENTACT.ENT.PRO.SEP.2019.05
	Version: 2.0, 27Aug2020
	Page: Page 40 of 94

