## 9.1.2 Treatment/Operation Visit (Visit 2)

- 1. Query subject regarding any changes in general health and the use of concomitant medications.
- 2. Commence treatment/operation.
- 3. Confirm eligibility criteria
- 4. If any adverse device effects or device deficiencies are observed or reported, they must be recorded as instructed in **Section 12**, adverse events and device deficiencies. Also record concomitant medications/therapies used to treat AEs.
- 5. Record Intra-operative delivery success, total operation time and Intra-operative time for operative closure with ENTACT septal stapler.
- 6. Record device identification information for the stapler (e.g., Unique Device Identifier, Lot Number, Serial Number, Catalogue Number) and the number of staples used.
- 7. Instruct the subject on proper postoperative care/procedures, including any contraindicated treatments/medication(s).
- Instruct the subject on follow-up procedures, including returning the treatment facility in 5 days (± 2) days for follow-up visit.
- 9. Complete Operation and Discharge Visit CRFs.
- 10 If applicable, complete an End of Study CRF.

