## 10.2 ANALYSIS POPULATIONS

The following analysis populations will be used for this study:

- Safety population (SAF): This includes all patients who have received the study device.
- Full Analysis Set (FAS): This includes all patients who were recruited into the study and have at least one post-baseline visit.
- Per-Protocol (PP) population: This includes all subjects in the FAS who have no significant protocol deviations and who meet all the inclusion/exclusion criteria.

Statistical analysis will be performed using each of the patient populations as follows: Analysis of the primary and secondary endpoints will be performed separately using both the FAS and PP populations. All safety analyses will utilize the SAF population.

This document contains information that is confidential and proprietary to Smith + Nephew PLC and Smith + Nephew, Inc. and is intended for use only by Smith + Nephew and its manufacturer. It shall not be reproduced or copied in whole or in part, nor shall the contents be disclosed by any means without prior written permission from Smith + Nephew, nor shall anyone make any use of it that is contrary to the expressed or implied wishes of Smith + Nephew.

Study Protocol	> ∕ smith&nephew
A prospective, multi-center, single arm PMCF study to evaluate the safety and performance of ENTACT™ (Next Generation) resorbable septal staple system for septoplasty	Number: ENTACT.ENT.PRO.SEP.2019.05
	Version: 2.0, 27Aug2020
	Page: Page 55 of 94

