## 10.4.2 Analysis of Secondary Endpoints

Nasal cavity assessments at day 5 and day 42 will be summarized and presented as count and percentage of each criterion.

Successful staple deployment at the operative visit will be summarized by count and percentage. A 95% exact confidence interval for a single proportion will be presented for successful staple deployment using the Clopper-Pearson method. The number of staples used and whether the stapler misfired will also be presented.

Total operating room time will be calculated and summarized using descriptive statistics and will be presented descriptively by septoplasty only cases as well as septoplasty and turbinate reduction cases.

Intra-operative time to deploy staples to complete septoplasty, calculated as time between start of closure to when the stapler was handed back to the scrub nurse, will be summarized and presented descriptively by septoplasty only cases as well as septoplasty and turbinate reduction cases.

NOSE score will be calculated and summary statistics will be presented by visit. Change in NOSE score from the pre-operative visit to each post-operative visit will also be presented and an ANOVA model will be used to assess statistical significance.

This document contains information that is confidential and proprietary to Smith + Nephew PLC and Smith + Nephew, Inc. and is intended for use only by Smith + Nephew and its manufacturer. It shall not be reproduced or copied in whole or in part, nor shall the contents be disclosed by any means without prior written permission from Smith + Nephew, nor shall anyone make any use of it that is contrary to the expressed or implied wishes of Smith + Nephew.

Study Protocol	% smith&nephew
A prospective, multi-center, single arm PMCF study to evaluate the safety and performance of ENTACT™ (Next Generation) resorbable septal staple system for septoplasty	Number: ENTACT.ENT.PRO.SEP.2019.05
	Version: 2.0, 27Aug2020
	Page: Page 57 of 94

The VAS Pain score will be summarized by visit. Change in VAS Pain score from the preoperative visit to each post-operative visit will also be presented and an ANOVA model will be used to assess statistical significance.

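### Exclusion 2 can be applied during surgery, so a patient sutured after a stapler failure may be reclassified as a replaceable screen failure and leave the success rates

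*Combined protocol and SAP*

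**What the plan says.** Section 7.3 (and the synopsis) makes a patient "ineligible for the study if he or she meets any of the following exclusion criteria at the baseline screening or during surgery". Criterion 2 on that list reads "Traditional suturing techniques is necessary". It gives no cause and no time point.

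Five other places bear on what happens next:

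- **9.1.2 (Visit 2).** Step 2 is "Commence treatment/operation" and step 3 is "Confirm eligibility criteria".
- **7.6.** Consented subjects who "have been treated with the study product are considered enrolled". The word *treated* is not defined.
- **7.7.** A consented subject who fails eligibility, or is not enrolled, for whatever reason is a consented screen failure. "Consented screen failures will be replaced without limit by newly enrolled subjects".
- **10.2.** The safety set is defined by "This includes all patients who have received the study device". The FAS takes recruited patients (also undefined) with at least one post-baseline visit. The PP set takes FAS patients who satisfy every inclusion and exclusion criterion and have no significant deviation.
- **10.4.1 and 10.4.2.** The FAS is the primary analysis population and PP is the sensitivity analysis. "Successful staple deployment at the operative visit will be summarized by count and percentage", with a Clopper-Pearson interval.

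**The concern.** No rule separates suturing that the surgeon finds necessary before trying the stapler from suturing that becomes necessary because the stapler jammed, misfired or did not close the flaps. On the wording, the second patient also meets exclusion 2, and meets it during surgery. If that patient is closed out as a screen failure, eligibility has been decided by the outcome that the study is meant to measure.

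This matters more here than in most single-arm device studies. Section 6.1.3 says that the staple is unchanged and that the changes are in the delivery part of the device. Failure to deliver staples at surgery is therefore the failure most specific to the new design, and it is the one that these rules can take out of the denominator. Up to three sites could also classify the same event differently, each after seeing whether the device had worked.

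**Working it through.** **Step 1: apply the rules to three patients.** All have consented and all end up sutured.

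| | A: need seen before stapler is introduced | B: stapler introduced, no staple placed | C: some staples placed, then sutured |
|---|---|---|---|
| Exclusion 2 (7.3) | met | met as worded | met as worded |
| Enrolled (7.6) | no | open: *treated* undefined | can be read as yes |
| Screen failure, replaced (7.7) | yes | permitted | permitted by the eligibility limb, in conflict with 7.6 |
| Safety set (10.2) | no | open: *received* undefined | yes |
| FAS (10.2) | no | no, if closed out at surgery; possible if seen again and counted as recruited | same as B |
| PP (10.2) | no | no | no |

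A is an ordinary screen failure. B and C are the gap: nothing in the protocol says that an attempted but failed stapling stays in the study or how it is scored.

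**Step 2: inputs for the size.** Section 11 plans 36 evaluable subjects and 10% dropout: 36 / (1 − 0.10) = 40 enrolled. Its assumed success rate is 92%, and 0.92 × 40 = 36.8, so 37/40 is the nearest whole count. The interval is Clopper-Pearson (10.4.1, 10.4.2): lower limit = 2.5% quantile of Beta(x, n − x + 1); upper limit = 97.5% quantile of Beta(x + 1, n − x). The number of device-failure conversions, k, is an assumption, because the documents give no rate for this device. I show k = 0 to 4 for the primary rate and k = 2 for deployment.

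**Step 3: deployment success, k = 2.** Assume that all 40 retained patients had successful deployment.

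- Reported after replacement: 40/40 = 100%, lower limit 0.025^(1/40) = 91.2%.
- All attempted: 40/42 = 95.2% (83.8 to 99.4).

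**Step 4: primary success, with each device-failure conversion counted as non-success.**

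| k | All attempted | Exact 95% CI |
|---|---|---|
| 0 (as reported) | 37/40 = 92.5% | 79.6 to 98.4 |
| 1 | 37/41 = 90.2% | 76.9 to 97.3 |
| 2 | 37/42 = 88.1% | 74.4 to 96.0 |
| 3 | 37/43 = 86.0% | 72.1 to 94.7 |
| 4 | 37/44 = 84.1% | 69.9 to 93.4 |

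Each replaced conversion is worth about 2 percentage points. At k = 2 the difference is 92.5 − 88.1 = 4.4 points.

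**Step 5: the same patients retained, with no added scoring rule.** None of the five Day 21 items in 8.3.1 concerns deployment or conversion. Two sutured patients with good healing could both score as successes: (37 + 2)/42 = 39/42 = 92.9%. The drop in step 4 therefore needs two things: keeping the patients in the denominator, and counting the conversion as non-success.

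**The case against.** The natural reading of exclusion 2 is a surgical need for sutures that has nothing to do with the device and may only become clear during the operation. The rest of the protocol fits that reading. Section 9.1.2 records delivery success, device deficiencies, device identifiers and staples used. Section 10.4.2 reports misfires and puts an interval on deployment success. Section 12.3 requires every device deficiency to be recorded. These analyses presuppose that failed deliveries stay in the data. The study product is the stapler, so a patient in whom it was used and jammed can readily be called treated. The PP set is only a sensitivity analysis, and section 11 sets a precision target, not a pass mark.

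Much of this stands, and it rules out four stronger statements that a reader might infer:

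- *The rules remove stapler failures from every population.* They permit it. *Treated*, *received* and *recruited* are undefined, so removal is not certain.
- *Failures would go unrecorded.* The operative, misfire and deficiency records would still exist. They do not feed the primary rate.
- *The literature in 4.2.2 gives a conversion rate.* It reports a jam with a perforation in 1 of 8 patients, and a malfunctioning first lot in a 24-patient series, both with 2009 devices. Neither is reported as a conversion to suture, and 4.2.1 gives complete coaptation in all 24. No expected number of replaced patients can be drawn from these reports.
- *The population rules alone move 88.1% to 92.5%.* Step 5 shows that they do not.

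What the objection does not supply is any sentence that keeps the attempted patient in the FAS. Section 10 leaves detail to a SAP finalized before database lock, but a SAP cannot recover follow-up for a patient closed out on the day of surgery.

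**Conclusion.** The point holds as a gap in the rules. Sections 7.3, 7.6, 7.7 and 9.1.2, read together, allow a site to turn a stapler failure that ends in suturing into a replaceable screen failure. Where that is done, the primary success rate (FAS and PP) and the deployment-success rate are conditional on the device having worked.

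The size is illustrative. It rests on an assumed two replaced patients out of 42 attempted: deployment 95.2% shown as 100%, and primary success 88.1% shown as 92.5%. The primary figure also assumes that a conversion for device failure is scored as non-success, which the current endpoint does not say. With no such conversions there is no effect.

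**What to change.** These changes concern study classification and analysis only, not how the patient is treated.

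1. **7.3 and 7.7:** state that exclusion 2 can make a patient a replaceable screen failure only if the need for suturing is identified before the stapler is first introduced. A need that arises later is then an outcome, not an eligibility breach, and does not by itself remove the patient from the PP set.
2. **7.6 and 10.2:** count every consented patient in whom the stapler was introduced as enrolled, in the safety set and in the FAS denominator, whether or not a staple was deployed and without requiring a follow-up visit. Do not replace these patients.
3. **10.4.1 and 10.4.2:** count conversion to suture because of stapler failure as a deployment failure and as primary non-success. This is consistent with 10.4.1, which already limits two of the five components to device-related findings. Use of splints or packing, or suturing unrelated to the device, should not be an automatic primary failure.
4. **Reporting:** list all intra-operative exclusions with reasons.

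The cost is protocol wording plus one scoring rule for the primary endpoint, with no added visits, procedures or patients. The reported success rate may be slightly lower. Section 21.1.3 says that Version 2.0 takes effect before enrollment, so if enrollment has not begun the change can precede any data.
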